All surgical procedures were performed by the same surgeon in both groups. In the scalpel group, second stage surgical procedures were carried out with standard technique. Local anesthesia was performed with 2ml of 40mg/ml articaine+ 0,012 mg/ml epinephrine (Maxicaine Fort, Vem İlaç San. ve Tic. Ltd. Şti, İstanbul, Türkiye) preoperatively. Incision was made on the area where the closure screw was reflected from the overlying mucosa and the closure screw was exposed. After insertion of the appropriate healing abutment, the procedure was completed by suturing if necessary. In the laser group, Er,Cr:YSGG laser (WaterLase iPlus; USA Biolase Technology Inc., Irvine, CA) with wavelength of 2780 nm was used on "implant recovery" setting suggested by the manufacturer and according to the recommended guidelines (pulse duration of 140–200 μ s, repetition frequency of 100 Hz, H mode, output power of 2.75 W, and air/water proportion of 10/10%). MZ5 application tip was used in non-contact mode with target tissue to expose the closure screw and the appropriate healing abutment was placed.

Before the operation, all patients were informed about the method by which the implants would be exposed and informed consent was obtained from all participants. The patients were taken to the waiting room on the day of the second stage implant surgery and were asked to fill the STAI and DAS questionnaires for evaluating their anxiety levels. The STAI questionnaire was repeated in the control session (Post-op STAI) one week after the operation in order to verify whether the anxiety levels depend on the patient's general anxiety or due to the surgical procedure. In addition, demographic information such as age and gender, daily analgesic use after the operation and VAS scores during the operation and on the 1st, 2nd and 3rd days after the operation were recorded. Patients were

divided into four groups according to analgesic use. Surgical procedures and patient evaluations (preoperative and postoperative) were performed by different physicians due to single-blind study design.

Evaluation of Anxiety

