STAI questionnaire, consisting of two parts with twenty questions each, was used to evaluate the level of state and trait anxiety in the participants (STAI-S: STAI State questionnaire and STAI-T: STAI Trait questionnaire). Both parts were evaluated separately. Patients' answers to each question were scored between 1-4 points. A total of 20-37 anxiety scores were assessed as minimum level of anxiety or none, 38-44 points as moderate and 45-80 as high.

In order to evaluate dental anxiety before treatment, DAS questionnaire consisting of 4 items including multiple choice answers was used. Patients' answers to questions were scored between 1-4 points. The total score of the questions in the questionnaire ranged from 4 to 20, and 4-11 points were interpreted as low level dental anxiety, 12-14 points as moderate and more than 14 points as high.

Statistical Analysis

In the evaluation of the demographic data Chi-squared test was used for the categorical variables to analyse the frequencies and ratios. For continuous variables, Student's t-test was used when normal distribution was provided and Mann-Whitney U test was used when normal distribution was not provided. In the evaluation of DAS findings, anxiety levels in each group were examined by Chi-squared test. However, Mann-Whitney U test was used to determine the differences between the groups. VAS findings were analyzed by considering the generalized linear mixed model (GLMM) method based on Poisson distribution and AR (1) variance covariance matrix. Correlated p values obtained from the Holm-Tukey multiple comparison method were used for the comparisons of the least squares means in GLMM. In the GLMM model, the effects of the variables (group, time and analgesic consumption) on VAS values and their interactions were modeled. In the analysis of the findings of the STAI-S and STAI-T scales, the cross tabulations of the groups and anxiety categories were examined by the Chi-squared test. Mann-Whitney U test was used for comparisons between groups, and Wilcoxon test was used for intergroup comparisons. p values < 0.05 and 0.01 were accepted as statistically significant. All statistical analyzes used in the study were performed on the SAS 9.4 software. In the determination of the power of the statistical tests, the SAS software was used for VAS variables, and the G*Power software was used for the STAI S and T variables.

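### Analgesic use is recorded daily but never compared between laser and scalpel; it enters only as a covariate for VAS, where it can shrink or distort the pain comparison

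*Combined protocol and SAP*

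**What the plan says.** The Study protocol section of the combined protocol and SAP states that "daily analgesic use after the operation and VAS scores during the operation and on the 1st, 2nd and 3rd days after the operation were recorded". It then says that patients were "divided into four groups according to analgesic use". No drug, unit, cut-point or time window is given for the four groups.

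In the Statistical Analysis section, VAS is analysed by a "generalized linear mixed model (GLMM) method based on Poisson distribution and AR (1) variance covariance matrix". Within that model, "the effects of the variables (group, time and analgesic consumption) on VAS values and their interactions were modeled". Multiplicity-adjusted p values "were used for the comparisons of the least squares means in GLMM".

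That is the only place in the section where analgesic consumption appears. The remaining named tests are for demographic data, DAS and the two STAI scales. On the first of these the wording is: "In the evaluation of the demographic data Chi-squared test was used for the categorical variables".

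**The concern.** VAS on days 1 to 3 measures the pain that remains after any analgesic has been taken. Analgesic need is the other part of the same outcome. If one method of exposing the implant hurts more, the difference may show in VAS, in analgesic use, or partly in each.

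The plan estimates only the first part, and does so after conditioning on the second. Analgesic use is observed after randomisation and is itself a response to pain. Comparing the arms at the same level of use therefore compares patients selected by something that the treatment may have changed. The arm effect from such a model is no longer the randomised comparison and can be biased in either direction.

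At stake is any conclusion about post-operative pain. The plan intends one: VAS has its own model, its own multiplicity method and a power statement. As written, the trial could miss or misstate a pain difference that its own recorded data would show.

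**Working it through.** **1. What is specified.** Analgesic use is recorded daily and also grouped into four. The only analysis that uses it has VAS as the response. No sentence has analgesic use as the response and arm as the factor, and no rule says how the two are read together. It is also unclear whether the daily data or the four groups enter the model. Post-operative use cannot explain VAS during the operation, yet the model sentence makes no exception for that time point.

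**2. The plan's own figure.** There is none on this point. The sample size (36 per arm, raised to 48) concerns dental anxiety. The checks below therefore use assumed values. From the documents they take only the form of the variables (VAS modelled as Poisson, four analgesic categories) and, in steps 5 and 6, the numbers operated: 38 scalpel, 44 laser.

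**3. Equal VAS, unequal analgesic use.** Large-sample simulation, 400,000 patients, one observation each:
- patient factor u ~ N(0,1);
- category = round(1 + 0.8 × arm + 0.7u + N(0, SD 0.7)), limited to 0–3;
- VAS ~ Poisson(2·exp(bu)), the same in both arms.

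Mean category is 1.06 v 1.76. The VAS ratio (higher-use arm over the other) is:

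| b | without analgesic | with analgesic category |
|---|---|---|
| −0.3 (heavier users report lower VAS) | 1.00 | 1.16 |
| 0 (unrelated) | 1.00 | 1.00 |
| 0.3 (heavier users report higher VAS) | 1.00 | 0.86 |
| 0.5 (same, stronger) | 1.00 | 0.78 |

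In the last two rows the arm that needed more analgesic looks better.

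**4. A true difference in underlying pain.** Underlying pain is gamma with mean 3, plus 1 in the worse arm, so the true ratio is 4/3 = 1.33. Category = round(s × (pain − 2) + noise), limited to 0–3. VAS ~ Poisson(pain − r × category).

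| relief r | s, noise SD | without analgesic | with analgesic category |
|---|---|---|---|
| 0 | 0.7, 0.3 | 1.33 | 1.07 |
| 0 | 0.7, 1.0 | 1.33 | 1.20 |
| 1.0 | 0.7, 0.3 | 1.17 | 1.11 |
| 1.0 | 0.7, 1.0 | 1.24 | 1.31 |
| 1.5 | 0.7, 0.3 | 1.04 | 1.14 |
| 1.5 | 0.7, 1.0 | 1.14 | 1.37 |

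Neither column is reliable alone. The unadjusted ratio falls as the analgesic works better. The adjusted ratio may be too low, close or too high, depending on dosing behaviour that the documents do not describe.

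**5. Power at 38 v 44.** Assumptions: underlying pain with SD 2 on 0–10, arm difference 1.3 before truncation, 0–3 doses driven by pain, and relief per dose of 0, 0.5, 1.0 or 1.5 points.
- Unadjusted Mann-Whitney on VAS (not the planned test): 78%, 74%, 67%, 39%. Under another dosing rule: 77%, 76%, 62%, 30%.
- One-day Poisson model with analgesic category (a simplification of the planned model): 16–24% in one set of runs and 19–23% in another, but 44–52% with noisier dosing.
- One-day linear model with dose category: estimated arm difference 0.37, 0.34, 0.36, 0.32, with power 25–29%. Against 1.3 that is between 0.32/1.3 = 25% and 0.37/1.3 = 28% of the true difference.
- Mann-Whitney on doses by arm: 65–68%, falling to 41–49% when the dosing-noise SD is raised from 1 to 2.

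**6. What an arm comparison could show.** For any analgesic use v none, two-sided α = 0.05:

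power = Φ[(|p1 − p2| − 1.96·SE0)/SE1], with SE0 from the pooled rate and SE1 from the separate rates.

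For assumed rates of 50% v 20%: pooled rate (19 + 8.8)/82 = 0.339; SE0 = √(0.339 × 0.661 × (1/38 + 1/44)) = 0.105; SE1 = √(0.25/38 + 0.16/44) = 0.101. Then (0.30 − 0.205)/0.101 = 0.94, and power is 0.83. Likewise 0.79 for 60% v 30%, 0.65 for 50% v 25%, and 0.51 for 40% v 20%. The comparison is informative for large differences only, which is why an interval is needed beside the test.

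**The case against.** A reader might infer that the plan would simply read equal VAS as equal pain. The documents do not support that. The planned model does not compare VAS alone: it conditions on analgesic use with interactions, so equal raw VAS need not give equal least-squares means, and no sentence equates the two. For the same reason the fall in unadjusted Mann-Whitney power from 78% to 39% does not describe the plan. In the simplified adjusted models that decline with dose effect is largely absent, and power is low throughout. The fault lies in conditioning on a response to pain and in the missing arm comparison.

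A reader might also infer that analgesic use was unrestricted, or that the daily records were discarded in favour of the four groups. The documents describe no regimen, free or fixed, and do not say that daily data were dropped. Neither inference is needed here.

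The Chi-squared sentence for categorical demographic data might have been meant to cover the four groups. This is possible but strained: the Study protocol section lists analgesic use beside demographic information, not as part of it. Even on that reading the groups are undefined.

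Two further objections stand in part. The trial is about dental anxiety, so pain is a supporting outcome. And every simulated size depends on assumed dosing behaviour, including the power of the remedy.

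**Conclusion.** The point stands as a change that should be made, limited to the pain outcome; the anxiety comparisons are unaffected. That no arm comparison of analgesic use is named, that its only stated role is explanatory, and that the four groups are undefined all follow from the text. That conditioning on a post-randomisation response can distort the arm effect follows from the design.

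The size is not fixed by the documents. Under the assumptions shown, the adjusted VAS ratio ranges from 1.16 to 0.78 when raw VAS is equal. A one-day model with analgesic category has about 16–24% power for a difference of 1.3 points in underlying pain, or 44–52% with noisier dosing. These models omit the repeated measures and the interactions of the planned GLMM, so they show direction and plausibility, not the trial's actual error.

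**What to change.** 1. Name analgesic use as a secondary outcome. Keep the daily amount in one unit for all patients, and define the four groups if they are retained.
2. Compare laser with scalpel on the 3-day total, using the Mann-Whitney test already in the plan and a 95% CI for the difference. Present the per-day amounts descriptively, which avoids a further multiplicity problem.
3. Report the VAS arm comparison also from a model without analgesic use. State which form of the analgesic variable enters the planned model, and do not use post-operative consumption to explain VAS during the operation.
4. State that VAS and analgesic use are interpreted together, so that similar VAS with unequal use is not reported as equal pain.

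A combined score (the sum of each patient's VAS rank and analgesic rank) is an optional supportive analysis.

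The cost is a few sentences, one more secondary outcome and a few extra tests on data already recorded. No change to what patients may take is proposed.

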**Evaluation of Dental Anxiety in Patients Undergoing Second Stage Surgery with Er,Cr:YSGG Laser
Treatment: Randomized Clinical Trial**

Approval Date: 24/11/2017

Study protocol

This study was carried out on 96-healthy individuals, aged between 20-75 years, who underwent dental implant therapy in XXX University, Faculty of Dentistry, Departments of Oral and Maxillofacial Surgery and Periodontology and whose healing caps will be placed after second stage implant surgery. The findings of Eroğlu et al. were used to determine the sample size. According to this, it was calculated that 36 patients each should be included in the experimental and control groups in order to determine a 50% decrease in dental anxiety levels (β : 0.8, α :0.05). Considering the possible follow-up losses, it was decided that both groups consist of 48 patients. 96 patients were divided into two groups by randomization procedure (GraphPad Prism). The study was approved by XXX University, Faculty of Medicine, Ethics Committee of Clinical Research (XXX-01-24.11.2017). Authors declare that there was a preoperative information performed to all of the patients. All surgical procedures were carried out in accordance with the Helsinki Declaration. The osseointegrated implants embedded under the oral mucosa were exposed with a scalpel (Group 1) or Er,Cr:YSGG laser (Group 2). Totally-304 osseointegrated implants in 96 patients were evaluated clinically and radiographically in detail before the second stage surgical procedures. Patients without sufficient-keratinized gingiva at the implant shoulder region, those the tissue transposition techniques should be applied, those with high DAS score, implants that can not be localized due to gingiva thickness, implants with the possibility of bone overlap on closure screw and scalpel incisions greater than 1cm length (per implant) were excluded. For these reasons, 10 patients in Group 1 and 4 patients in Group 2 were excluded from the study. After all these evaluations, the second stage implant surgery was initiated with scalpel for 172 osseointegrated implants in 38 patients. The second stage implant surgery of 106 osseointegrated implants (Implant Direct, CA, USA) in 44 patients was performed with Er,Cr:YSGG (Figure 1).

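### The Poisson mixed model ties the variance of a bounded VAS rating to its mean, and the plan omits the details needed to show that its pain contrasts hold their error rate

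*Combined protocol and SAP*

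**What the plan says.** The Study protocol section states that "VAS scores during the operation and on the 1st, 2nd and 3rd days after the operation were recorded", which gives four occasions per patient. It gives no range, unit or anchors for the VAS. Surgery was started for "172 osseointegrated implants in 38 patients" in the scalpel group and "106 osseointegrated implants (Implant Direct, CA, USA) in 44 patients" in the laser group.

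The Statistical Analysis section analyses VAS by a "generalized linear mixed model (GLMM) method based on Poisson distribution and AR (1) variance covariance matrix". In it, "the effects of the variables (group, time and analgesic consumption) on VAS values and their interactions were modeled". P values for group and time comparisons come from the "Holm-Tukey multiple comparison method were used for the comparisons of the least squares means in GLMM". On significance, "p values < 0.05 and 0.01 were accepted as statistically significant".

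The section does not state:
- the link function;
- whether AR(1) describes the residuals or the random effects;
- whether a scale (overdispersion) parameter is estimated;
- whether standard errors are model-based or robust;
- any check of dispersion, or any reason for a count distribution.

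**The concern.** A Poisson variance equals the mean or, with an estimated scale, is proportional to it. That is natural for a count. A VAS score is a position on a bounded line, and its SD need not follow its mean in that way. Where the assumed variance is too small, the standard error is too small and false positives exceed 5%. Where it is too large, real differences are harder to detect.

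A fixed scale adds a second problem. Rewriting the same pain in millimetres instead of centimetres multiplies the mean by 10 and the variance by 100, so identical data give different p values.

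The group-by-time least squares means of VAS are what a statement about less pain with the laser would rest on.

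**Working it through.** **Plan's own figure.** There is none to reproduce. The sample size of 36 per group concerns anxiety. The documents give no VAS mean, SD, power or error rate beyond the nominal level.

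**Inputs from the documents.** 38 and 44 patients; four occasions; level 0.05, taken as two-sided.

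**Assumptions.** Log link; a 0-10 or 0-100 scale; means 2, 3, 2, 1 on 0-10 in time order; no group effect; a full group-by-time model without analgesic terms; rates before Holm-Tukey adjustment.

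**Formula.** With residual-side AR(1) the fitted means are the cell means.
- Model variance of a log cell mean: phi/(n·mu).
- True variance: SD²/(n·mu²).
- Ratio of true to model variance: R = SD²/(phi·mu). The group sizes cancel.
- Error rate: 2·[1 − Φ(1.96/√R)]. This is 5% only when R = 1.

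**Case 1: scale fixed at 1.** Going from 0-10 to 0-100 multiplies R by 100/10 = 10. At the peak (mean 3), with SD 40% to 80% of the mean:
- 0-10: R = 0.16 × 3 = 0.48 to 0.64 × 3 = 1.92, so error is 0.5% to 16%.
- 0-100: R = 4.8 to 19.2, so error is 37% to 65%.

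**Case 2: one residual scale estimated.** Here phi is the average of SD²/mu over the four times, so the unit and the overall size of the SD cancel.

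| Variance pattern | R at means 2, 3, 2, 1 | Error rate |
|---|---|---|
| Proportional to mean | 1, 1, 1, 1 | 5%, 5%, 5%, 5% |
| SD proportional to mean: R = mu/2 | 1, 1.5, 1, 0.5 | 5%, 11%, 5%, 0.6% |
| SD constant: R = (1/mu)/0.583 | 0.857, 0.571, 0.857, 1.714 | 3.4%, 1.0%, 3.4%, 13.4% |
| Variance proportional to mu(10−mu): R = (10−mu)/8 | 1, 0.875, 1, 1.125 | 5%, 3.6%, 5%, 6.5% |

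**Check by simulation.** Bounded (beta) scores were simulated with within-patient AR(1) correlation 0.6 and 38 and 44 patients, 4,000 trials per scenario. With means 3, 2, 1.2, 0.6, SD 70% of the mean and an estimated scale, the formula gives 14.0%, 7.1%, 2.0%, 0.1%. The simulated rates on 0-100 were 14.5%, 7.1%, 1.9%, 0.1%. On 0-10, rounded to whole numbers, they were 12.1%, 5.6%, 1.7%, 1.2%.

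**Case 3: AR(1) on random effects only, no residual scale.** This was simulated with 400 trials per scenario, so a rate near 5% has a Monte Carlo standard error of √(0.05 × 0.95/400) = 1.1 percentage points.
- Means 3, 2, 1.2, 0.6, SD 70% of the mean: about 5%, 1.5%, 1%, 0.2% on 0-10 and 9%, 6%, 4%, 2% on 0-100.
- Means 4, 3, 2, 1.2, constant SD 1.2: at the lowest time, about 7% on 0-10 and 18.5% on 0-100.

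The unit therefore matters here too, though less than in Case 1.

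**Robust standard errors.** In the 4,000-trial simulations the sandwich error was 4.8% to 7.3% at every time, in both units and all five SD patterns tried.

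**The case against.** The strongest reply is that the text may describe a sound analysis. AR(1) may be on the residual side with an estimated scale, in which case the unit drops out. If variance is also roughly proportional to the mean, the error is nominal. A mu(10−mu) variance, a natural shape for a bounded rating, moves it only to between 3.6% and 6.5%. All of this stands.

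The rates above also precede the Holm-Tukey step. Take four group contrasts as the family, which is an assumption because the plan does not define one. The first Holm step then tests at 0.05/4 = 1.25%, critical value 2.498. With R = 1.5 the real rate is 2·[1 − Φ(2.498/√1.5)] = 4.1%. So 11% is not the rate at which the plan would declare a false peak difference. But 4.1% is still more than three times the intended 1.25%, because the adjustment works on p values whose standard errors are already wrong.

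A reader might infer three stronger things, none of which the documents support:
- **That false positives gather at the pain peak and favour a laser claim.** This needs SD to rise in proportion to the mean. With constant SD the pattern reverses.
- **That the false-positive rate is 37% to 65%.** This needs both a scale fixed at 1 and a 0-100 VAS, and neither is stated. A random-effects AR(1) does not force the marginal variance to equal the mean, and its simulated rates were far lower.
- **That the error must be wrong even with an estimated scale.** It is not wrong when variance is proportional to the mean.

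**Conclusion.** The concern holds in conditional form. The model ties VAS variance to its mean, and the plan leaves out the items that would show whether this does harm. With a fixed scale or AR(1) on random effects only, the error rate depends on the VAS unit. With one estimated residual scale it does not, but single time points can run from about 1% to 13% at a nominal 5% under the assumed means, in either direction, or stay at 5%.

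These sizes rest on assumed means and SD patterns, a log link, no analgesic terms and no multiplicity adjustment. The documents cannot settle size or direction. What can be said is that error control for the VAS contrasts is not shown. The anxiety comparisons, on which the sample size is based, are untouched, so this is an improvement that should be made and not a threat to the whole trial.

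**What to change.** Keep the log-mean model with its group, time and analgesic terms, and:
1. State the VAS unit and range.
2. Fit AR(1) on the residual side with an estimated scale, and say so.
3. Base the Holm-Tukey comparisons on patient-clustered robust (sandwich) standard errors with a small-sample correction (the EMPIRICAL option in SAS GLIMMIX). The simulated rates of about 5% to 7% are the reason for asking for the correction.
4. Report VAS means and SDs by group and time, so that the variance assumption can be seen.

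A normal repeated-measures model with unstructured covariance over the four occasions may serve as a sensitivity analysis. It should keep the analgesic terms. Preferring it as the main model would be partly a matter of taste.

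Cost: no new data, and a small change to an analysis already run in SAS 9.4 (the code is not shown, so this is a judgement). Intervals will become wider at some time points.

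### The only VAS model described conditions on post-operative analgesic use, so its group contrasts need not equal the overall difference in VAS between scalpel and laser

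*Combined protocol and SAP*

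**What the plan says.** All references are to the combined protocol and SAP.

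- **Allocation (Study protocol).** "96 patients were divided into two groups by randomization procedure". After exclusions of 10 and 4, surgery went ahead in 38 scalpel and 44 laser patients.
- **Data recorded (Study protocol).** The list includes "daily analgesic use after the operation and VAS scores during the operation", with further VAS scores on days 1, 2 and 3. Patients were also "divided into four groups according to analgesic use".
- **VAS model (Statistical Analysis).** The model is a Poisson GLMM with an AR(1) covariance matrix. Its terms are given as follows: "In the GLMM model, the effects of the variables (group, time and analgesic consumption) on VAS values and their interactions were modeled". Multiplicity-adjusted p values "were used for the comparisons of the least squares means in GLMM".
- **Other outcomes (Statistical Analysis).** For DAS, "Mann-Whitney U test was used to determine the differences between the groups". For STAI, "Mann-Whitney U test was used for comparisons between groups". Neither comparison has a post-operative term.
- **Power (Statistical Analysis).** "the SAS software was used for VAS variables". No power value or VAS effect size is given.

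The text does not give a VAS model without the analgesic term, a VAS estimand or a reason for the adjustment. Nor does it say whether the daily record or the four-group variable entered the model, which interactions were fitted, which least squares means were compared, or how they were weighted over analgesic categories.

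**The concern.** Analgesic use comes after both randomisation and surgery. Patients may take more because they hurt more, and what they take may lower the score. Comparing the groups at equal analgesic use then sets patients side by side who reached that use by different routes, and the balance given by randomisation no longer protects the comparison. A reader who takes the group or group-by-time result as the difference that the surgical method made to VAS could be misled either way. No simpler VAS analysis is described against which to check it.

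The intra-operative score adds a conditional problem. If the term is the patient-level four-group variable, the model explains pain during surgery by drug use that came later. The four-group sentence suggests this coding, but the documents do not confirm it.

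**Working it through.** There is no VAS figure in the plan to reproduce, and the sample size of 36 raised to 48 per group concerns anxiety. The check is therefore structural, with illustrations.

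**1. Order of events.** Randomisation comes first, then surgery with the intra-operative VAS, then analgesic use and VAS over days 1 to 3. The analgesic term is a post-randomisation variable whichever coding was used.

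**2. When the two contrasts agree.** Let category k have share s_k, scalpel mean m_k and laser:scalpel ratio r_k, with surgery not affecting use, so that the shares are equal in both groups.

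- Overall ratio = Σ s_k m_k r_k / Σ s_k m_k.
- Equally weighted least squares ratio on the log scale, four categories = (r_1 r_2 r_3 r_4)^(1/4).

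If every r_k equals r, both expressions equal r. If not, they can differ although use is the same in both groups. Assumed example: shares 0.1, 0.2, 0.3, 0.4; scalpel means 1.5, 2.5, 3.5, 5; ratios 0.5, 0.6, 0.8, 1.0.

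- Scalpel: 0.15 + 0.50 + 1.05 + 2.00 = 3.70.
- Laser: 0.075 + 0.300 + 0.840 + 2.000 = 3.215.
- Overall ratio: 3.215 / 3.70 = 0.87.
- Least squares ratio: (0.5 × 0.6 × 0.8 × 1.0)^(1/4) = 0.24^(1/4) = 0.70.

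Weighting by the observed shares removes the gap if fitted means are averaged on the VAS scale, since that returns 0.87. Averaging on the log scale gives exp(0.1 ln 0.5 + 0.2 ln 0.6 + 0.3 ln 0.8) = exp(−0.238) = 0.79, which still differs. The weights and the scale both matter, and neither is stated.

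**3. When surgery does affect use.** This is a simulation with every input assumed: Poisson VAS, a shared patient pain term, a four-level patient-level analgesic variable, true laser:scalpel ratio exp(−0.3) = 0.741, 100,000 per arm, equal weights.

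| Analgesic use depends on | Unadjusted post-operative ratio | Adjusted ratio |
|---|---|---|
| patient's pain only | 0.74 | 0.74 |
| group and patient's pain | 0.74 | 0.92 |
| group and patient's pain, and use lowers VAS | 0.83 | 0.92 |

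In the last two rows the intra-operative ratio also moves, from 0.74 unadjusted to 0.92 adjusted, although that score precedes any analgesic use.

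**4. Direction.** A second simulation let daily use follow daily pain. Assumed inputs: day 1–3 pain ratio 0.70; intra-operative ratio 1.00; median VAS 3; log SD 0.5; time factors 1, 1, 0.8, 0.6; latent AR(1) 0.6; Poisson VAS capped at 10; use categories cut at pain 2, 3 and 4.5; patient-level group equal to the rounded mean daily category; 500,000 per arm; full three-way model, equal weights. Fifteen settings crossed five relief multipliers per category with three levels of log noise in the link from pain to use. Day 1 ratios, unadjusted / adjusted, at the two ends of the relief range:

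| Noise SD | No relief (×1.0) | Strongest relief (×0.6) |
|---|---|---|
| 0.4 | 0.71 / 0.86 | 0.93 / 0.89 |
| 0.8 | 0.71 / 0.79 | 0.86 / 0.80 |
| 1.5 | 0.71 / 0.74 | 0.79 / 0.74 |

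Over all 15 settings the adjusted ratio was nearer to 1 in 9, within 0.01 in 1 and further from 1 in 5. The adjusted intra-operative ratio was 1.02 to 1.12 although the true value was 1.00. With use made independent of group, the two ratios agreed to within 0.003. That agreement is expected, because the simulation gives everyone the same log effect; it says nothing about the effect modification in step 2.

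**The case against.** **VAS is a supporting outcome.** The title, questionnaires and sample size concern anxiety, and no VAS objective or claim of a total effect is stated. Describing how VAS relates to analgesic use can be a legitimate aim. This limits the reach of the point but does not remove it: VAS is formally tested with multiplicity-adjusted comparisons, and the analgesic model is the only one described.

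**Analgesics distort VAS, so one should adjust.** Analgesic use is a response to pain after allocation, not a baseline confounder. It is true, however, that the unadjusted contrast reflects pain under the analgesics actually taken. In the second simulation strong relief moved it to 0.93 against an assumed pain ratio of 0.70. It has to be read beside analgesic use.

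**The numbers prove little.** This stands. Every input is assumed, the 9/1/5 count depends on the grid chosen (with an analgesic main effect only it becomes 11/3/1), and the adjusted day 1 ratio stayed below 1 throughout. No p values at 38 v 44 were computed, so no changed conclusion is shown.

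**The simpler model does not restore the full randomised comparison.** This also stands. The exclusions of 10 and 4 include a criterion on scalpel incision length, worded for one arm. Implants per patient also differ: 172/38 = 4.5 against 106/44 = 2.4. These are separate matters that the change proposed here leaves untouched.

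Three stronger readings might be inferred, and the documents support none of them. The first is that the reported VAS result is wrong in a known direction; there are no data on analgesic use by group. The second is that equal analgesic use alone would make the adjusted and unadjusted contrasts agree; the example giving 0.87 and 0.70 shows otherwise once interactions are fitted. The third is that the intra-operative score was certainly modelled on a later event; that depends on a coding that is not stated.

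**Conclusion.** The point holds as a structural one, with high confidence: the VAS group and group-by-time contrasts are conditional on a post-randomisation variable and need not equal the overall between-group difference. They can be expected to agree only if surgery does not affect analgesic use and, in addition, the group effect does not vary by analgesic category or the fitted means are averaged on the VAS scale over the observed shares. The documents establish none of these.

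Size and sign cannot be determined. The simulated ratios show that a gap can arise in either direction; they assume no effect modification and do not estimate this trial's error. The reach is VAS only, in 38 + 44 = 82 patients. The change should be made, but nothing here touches the STAI or DAS analyses or the sample size.

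**What to change.** 1. Make the main VAS model group, time and group by time, as a Poisson GLMM with within-patient AR(1) and no analgesic term. State which least squares means are compared; the existing multiplicity method can be kept.
2. Compare analgesic use between groups as a separate, named outcome, and read the VAS result beside it.
3. Keep any analgesic-adjusted model as exploratory. State its coding (daily or four-group), its interactions, and the weights and scale of its least squares means. Leave the intra-operative VAS out of it.
4. Describe the result as a between-group contrast in the 82 patients operated on (38 v 44, after exclusions of 10 v 4), not as the effect in all 96 randomised.

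The cost is one simpler re-analysis of data already collected and revised wording of the VAS methods and results. Because the analysis is described as already done, the VAS conclusions may change. No new data are needed.
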